HRP-503B – BIOMEDICAL RESEARCH PROTOCOL
(2017-1)

Protocol Title: Neurofeedback of amygdala activity for PTSD

Principal Investigator: [name]

Version Date: 11/08/2022

(If applicable) ClinicalTrials.gov Registration #: NCT03574974

INSTRUCTIONS

This template is intended to help investigators prepare a protocol that includes all of the necessary information needed by the IRB to determine whether a study meets approval criteria. **Read the following instructions before proceeding:**

1. Use this protocol template for a PI initiated study that includes direct interactions with research subjects. Additional templates for other types of research protocols are available in the system Library.
2. If a section or question does not apply to your research study, type “Not Applicable” underneath.
3. Once completed, upload your protocol in the “Basic Information” screen in IRES IRB system.

SECTION I: RESEARCH PLAN

1. Statement of Purpose: State the scientific aim(s) of the study, or the hypotheses to be tested.

The primary purpose of this study is to investigate the efficacy of biofeedback (or neurofeedback; "NF") of real-time functional magnetic resonance imaging (rt-fMRI) data for reducing symptoms in patients with PTSD. The target mechanism for this intervention is control over amygdala activity following trauma recall. Namely, participants will be presented with rt-fMRI data that corresponds to amygdala activity in response to recalled trauma in order to help them improve control over this key region in the fear circuit. We hypothesize that improved control over the amygdala will reduce the core symptoms of PTSD and initiate a healthier clinical trajectory.

A secondary purpose of this study is to use fMRI as a method for investigating brain function in individuals with PTSD. This study approach provides a tool for probing the neurobiology of PTSD by (1) testing the critical role of the amygdala in this disorder and (2) examining how amygdala connectivity is related to both amygdala regulation and clinical symptoms.

In pursuit of the overarching goals of this study, we aim to:

- determine if our NF intervention increases control over the region of interest (the amygdala) more than sham feedback in which participants receive feedback that is unassociated with their PTSD symptoms
- determine if NF results in clinical improvements in PTSD symptoms, relative to sham feedback, and examine whether these improvements correlate with improved control over the amygdala
- determine if NF results in changes in resting state connectivity to the amygdala, and whether these changes correlate with symptom improvement and an improved ability to regulate the amygdala

Finally, we would like to relate genetic markers to brain patterns in PTSD subjects. Therefore, we have a created a separate consent form to allow us to collect, analyze, and relate genetic information to brain function.

2. Probable Duration of Project: State the expected duration of the project, including all follow-up and data analysis activities.

The initial R-61 phase (testing whether, when used by human participants, the proposed intervention alters the presumed biological signature/mechanism of action) will last two years. If in the R-61 phase, participants who receive NF demonstrate larger improvement in control over their amygdala than sham patients, an R-33 phase (continued testing of the efficacy of the intervention) will be initiated, and last up to 8 years.

3. Background: Describe the background information that led to the plan for this project. Provide references to support the expectation of obtaining useful scientific data.

MRI methods can detect quite subtle changes in blood flow/oxygenation using T2* weighted images. These methods are often used to assess alterations in brain that occur with regional activation in response to external stimuli or tasks. The methods, known generally as functional magnetic resonance imaging (fMRI), are non-invasive and permit repeated performances of tasks in individuals as well as children. The resolution is similar to that of conventional anatomic MRI. There is firm evidence that this approach to the study of brain responses provides a higher quality of information, with much better spatial and temporal resolution, sensitivity and safety, and without the need for inter-subject averaging, than the best PET or SPECT studies of

blood flow. For localization and quantitation of regional responses to stimuli, it is becoming increasingly clear that MRI will be the method of choice in experimental neuroscience. The preliminary results from other laboratories strongly suggest that this method is capable of providing unique information about the magnitude and location of the physiological response of the brain to specific stimuli [1,2].

More recently, there have been publications suggesting that real-time neurofeedback of functional imaging data can enable individuals to control brain activity in specific parts of their brain. One recent study reported that neurofeedback of anterior cingulate activity resulted in a decrease in pain in patients with chronic pain disorders as well as a decrease in the perception of pain associated with a painful stimulus in healthy control subjects [3]. Thus, real time neurofeedback of functional imaging data is new method with promising applications to many clinical conditions.

In the context of PTSD, real time fMRI neurofeedback may be effective at reducing symptom severity by targeting amygdala activity. Amygdala hyperactivity is a hallmark feature of PTSD, with a substantial body of literature revealing heightened amygdala responsivity in PTSD during the processing of both trauma-related and trauma-unrelated affective information [4]. Amygdala hyperactivity is also positively correlated with symptom severity in PTSD, making it an ideal target for neurofeedback aimed at producing clinical improvement (see Shin et al. for review) [4]. Moreover, amygdala activation is associated both with the risk of developing PTSD and with positive response to treatment, [5, 6], further highlighting the unique role of the amygdala in modulating PTSD. This study will target amygdala activity using a script paradigm first piloted by other groups [7, 8], in which individual trauma scripts are collected for each subject and later played in the scanner. This will allow us to localize and provoke amygdala activity to use as a target in the neurofeedback intervention.

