Over the course of this procedure, subjects will be asked to report various aspects of their experience – this will include responding to questions regarding their perceived control over their brain activity.

- i. In-Magnet Assessment 1: MPRAGE, Resting State, Initial Control Runs, and Localizer. If time allows, DTI data will also be collected.

During the first in-magnet assessment, a high resolution structural image will be collected using an MPRAGE sequence. Functional resting state data will be collected, as well as four control runs. During the resting state sessions spontaneous pupil dilation will be measured using a Eyelink 1000 system. As seen in Figure 2, control runs involve a resting period, exposure to a provocative audio clip, a period of down-regulation where participants try to bring down their amygdala activity, and a final resting period. In order to minimize anticipation and rumination regarding the upcoming or preceding stressor, resting periods are separated from the provocative audio clip and subsequent period of down-regulation by a 1-back memory task (seen in Figure 2 as “1-bk”). These memory tasks provide a cognitively-engaging distraction for the subject, preventing anticipatory and spill-over amygdala activity during resting periods and allowing for a more valid baseline to be established.

Rest	1-bk	Prov audio clip	Down-regulate	1-bk	Rest
60s	30s	60s	60s	30s	60s

Figure 2: Schematic illustration of a control task run. Control assessed based on activity in the target region of the amygdala in the down-regulate blocks (relative to rest)

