i. *Preprocessing:* Data will be motion corrected using SPM (<http://www.fil.ion.ucl.ac.uk/spm/>) and all subsequent analyses will be done using Yale BiolImage Suite software package.

- ii. *Registration:* The Montreal Neurological Institute (MNI) brain will be used as a reference coordinate system. Functional imaging data for all subjects will be transformed to the space of the MNI brain via a series of registrations (functional → anatomical → MPRAGE → MNI space) that have all been visually inspected.
- iii. *Localizer analyses:* The localizer run (see section I.4. *Research Plan*) will be used to define the target region for NF. First, a whole brain “t-map” will be computed by calculating voxel-wise t-tests contrasting activity during the trauma script exposure period to activity in the resting periods, after adjusting for hemodynamic delay. This is not a true t-map due to autocorrelation, but is useful for identifying the voxels with peak activation in the amygdala. The 30 peak voxels (subject to a cluster filter of 4) falling in the amygdala will be defined as the target area.

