- iv. *Control task activation analyses:* Control over the amygdala target region will be computed by running voxel-wise regression analyses separately for the two categories of traumas – trained (traumas with which the subject engaged in NF) and untrained (traumas that the subject was not exposed to during NF). Four regression analyses will be run per subject – one per category from each of the two assessment sessions. Regressors will be defined for the task periods using boxcar functions convolved with a canonical hemodynamic response function. Three regressors will be used, corresponding to the provocation block, the down-regulate blocks of interest, and the 1-back periods (the lattermost being included to remove the effects of the 1-back periods and make contrasts relative to the rest blocks). Resulting maps of beta values for the regulate and provocation blocks will be transformed to a common space (see above section I.b.) and masked with the target region (also transformed to common space). Average value in the target region will be computed separately from beta maps for the provocation and down-regulate blocks to yield estimates of activation in the amygdala in each condition of each assessment session for the trained and untrained trauma memories. **All analyses outlined in the following sections will use data from the regulation blocks of the untrained traumas unless otherwise noted.**
- v. *Resting state analyses:* In addition to the offline neuroimaging data analyses described above in section I., resting state data collected during each In-Magnet Assessment will be low-pass filtered (0.1 Hz), motion parameters, and the average time-courses of the ventricles and white matter will be regressed from the data. Seed maps of connectivity to the amygdala will then be computed. First, the time-courses of voxels in the target area will be averaged to yield a reference seed region time-course. This time-course will be correlated with the time-course of activity measured at every voxel in the brain to yield a whole-brain map of r-values. The r-values will be transformed to Gaussian variables via Fisher’s transform. The resulting seed region connectivity maps for each In-Magnet Assessment of each subject will be entered into group-level analyses after transformation to common space (see above section ii.).

B. R61 Phase:

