- i. *To determine if NF increases control over amygdala more than sham feedback:* Activation in the target region of the amygdala in the down-regulate blocks (computed as described in above section A.iv.) will be compared across groups to see if mean activation is larger in the NF group than the sham feedback group, with an effect size of the group difference $d > 1$. If so, this will satisfy “Go” criteria and the study will proceed to the R61 phase. If not, the decision will be “No Go”.

C. R33 Phase:

- i. *To determine if NF increases control over the amygdala significantly more than sham feedback:* Activation in the amygdala in the down-regulate blocks (computed as described in above section A.iv.) will be entered into a 2x2 ANOVA with factors time-point (2 levels: pre and post) and group (2 levels: NF and sham). If there is a significant interaction of group by time-point at a $p < 0.05$ level, a two-sample t-test will be used to see if the improvement in control was greater in the NF subjects than the sham subjects.

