- ii. *To determine if NF improves symptoms more than sham feedback and to correlate symptom changes with control over the amygdala:* A 2x2 ANOVA with factors group (2 levels: NF and sham) and time-point (2 levels: pre-intervention and first post-intervention) will be run on the past-month scores from the clinician-administered symptom checklist collected during the Full Clinical Assessment sessions. If there is a significant group-by-time-point interaction and post-hoc t-tests reveal a significantly greater improvement in symptoms in the NF group than the sham group, we will conclude the NF does improve clinical symptoms more than the sham. The change in score will also be correlated across NF subjects with the change in control over the brain area (computed as described above in section A.iv.). We hypothesize a decrease in score (indicating improvement in PTSD symptoms) will be correlated with an increase in control. A secondary analysis will be run using all 3 time points of scores collected (pre, 1 month post, and 2 month post intervention) to explore the long-term clinical effects. A linear mixed model analysis with group (NF or sham) by time-point (pre, 1 month post, and 2 month post intervention) will be used to capture the longitudinal effect of the clinical intervention. Finally, if the intervention does appear to reduce symptoms, we will explore whether these changes are greatest for scores on PTSD criterion B (intrusion) and criterion E (alteration in arousal reactivity) as these are expected to be most closely related to successful amygdala regulation.

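### The control-task analyses read only the amygdala target, so they cannot separate amygdala-specific control from a wider signal drop that is larger under NF than under sham

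*Combined protocol and SAP*

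**What the plan says.** Section I, item 1 names control over the amygdala as the target mechanism, hypothesises that better control reduces PTSD symptoms, and lists "testing the critical role of the amygdala in this disorder" among the secondary purposes.

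The readout is defined in three places:

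- Item 4.C.i, caption to Figure 2: "Control assessed based on activity in the target region of the amygdala in the down-regulate blocks (relative to rest").
- Item 13.A.iii: "The 30 peak voxels (subject to a cluster filter of 4) falling in the amygdala will be defined as the target area".
- Item 13.A.iv: the regressions are voxel-wise, the beta maps are then "masked with the target region (also transformed to common space"), and "Average value in the target region will be computed separately from beta maps for the provocation and down-regulate blocks".

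On the model terms, 13.A.iv states: "Three regressors will be used, corresponding to the provocation block, the down-regulate blocks of interest, and the 1-back periods". Removal of ventricle and white-matter signal appears only in 13.A.v, for resting-state data.

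The down-regulate mean then feeds three analyses: the Go criterion in 13.B.i (a group difference with d above 1); the group-by-time ANOVA in 13.C.i, headed "To determine if NF increases control over the amygdala significantly more than sham feedback"; and, in 13.C.ii, "The change in score will also be correlated across NF subjects with the change in control over the brain area".

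Under item 4.C.iii the sham arm does the same task with the subject's own audio clips. Only the source of the feedback line differs.

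**The concern.** The yoked sham isolates whether feedback is contingent on the subject's own signal. It does not isolate which part of the brain responds. Contingent feedback rewards any strategy that lowers the target signal, including one that lowers signal much more widely, such as disengaging from the material. Item 4.B says subjects experiment with strategies during feedback and learn which ones are effective. Sham subjects do not get that reinforcement, so a wide drop could develop in NF and not in sham.

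If it did, the Go rule and 13.C.i would count it as control over the amygdala. The correlation in 13.C.ii is more exposed because it has no sham comparison. NF subjects who disengage more could show both a larger signal drop and a larger fall in symptoms, and this would read as an amygdala mechanism.

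What is at stake is the mechanistic conclusion. The test of symptoms against sham does not depend on this readout.

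**Working it through.** **No figure to reproduce.** Section III, item 1 gives an enrolment target of 60 without power, SD or dropout. The d above 1 in 13.B.i is a decision threshold. The figures below therefore rest on stated assumptions.

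**Step 1: which drops reach the result.**

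| Source of a drop in target signal | Handled by | Passes into 13.C.i? |
|---|---|---|
| Equal in rest and down-regulate blocks | Contrast against rest (4.C.i, 13.A.iv) | No |
| Equal in both arms | Group-by-time interaction | No |
| Pulse or respiration noise | Recorded and used in processing (4.C) | Partly removed |
| Wider drop in the down-regulate block, larger in NF | Nothing planned | Yes |

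A simulation (20,000 runs, 30 per arm, two-sided 5%) confirms the second row. With an equal drop of 0.5 or 1.0 units in both arms, the target test favoured NF in 2.3% and 2.6% of runs, about the nominal 2.5% for one direction.

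For the correlation in 13.C.ii the second row is missing. Differences between NF subjects in the size of a wide drop enter it directly.

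**Step 2: size of the fourth row.** Assumptions: 30 per arm, effects in SDs of the change score, two-sided 5% test with 58 degrees of freedom, and the same shift everywhere in NF only. The probability of a significant result favouring NF is the upper tail of a non-central t with non-centrality d × √(30/2) = 3.873d.

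| Non-specific NF-only shift d | Non-centrality | Target test favours NF | Target minus comparison favours NF |
|---|---|---|---|
| 0.3 | 1.162 | 21% | 2.5% |
| 0.5 | 1.936 | 48% | 2.5% |
| 0.8 | 3.098 | 86% | 2.5% |

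The simulation used a different variance structure: global SD 0.5, target-specific SD 1.0, comparison noise SD 0.5. It gave 39%, 78% and 93% for NF-only drops of 0.5, 0.8 and 1.0 units, against about 2.5% on the difference. Its target SD is √(0.25 + 1) = 1.118, so those drops are 0.45, 0.72 and 0.89 SD. The two sets of figures agree.

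**Step 3: what the difference costs in power.** With equal SDs and correlation ρ between the two regions' changes, the SD of the difference is √(2(1 − ρ)). For a true effect of 0.8 SD in the target only (power 86% on the target):

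| ρ | SD of difference | Effect in those SDs | Power |
|---|---|---|---|
| 0 | 1.414 | 0.566 | 58% |
| 0.3 | 1.183 | 0.676 | 73% |
| 0.5 | 1.000 | 0.800 | 86% |
| 0.7 | 0.775 | 1.033 | 98% |

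**Step 4: why a non-significant difference must not be labelled non-specific.** Simulated under the same assumptions, these are the shares of trials with a successful target test whose difference does not reach significance:

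| True effect (target / elsewhere) | ρ = 0.3 | ρ = 0.5 | ρ = 0.7 |
|---|---|---|---|
| 0.8 / 0 SD | 21% | 10% | 2% |
| 0.8 / 0.3 SD | 59% | 47% | 27% |

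In every cell the target effect really is the larger one, so a non-specific label would be wrong.

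**The case against.** The strongest reply is that the plan answers the question it sets itself. The listed aim is more control over the region of interest than under sham, and 13.C.i tests exactly that. No passage claims that the effect is exclusive to the amygdala. Section V describes the mechanism as stronger emotion-regulation circuitry, so change outside the target is to be expected. The strategy session in 4.B precedes randomisation and is common to both arms. The figures in Step 2 are ordinary power with the effect relabelled, and nothing in the documents indicates how likely or how large an NF-only uniform shift would be. Thirty per arm and equal SDs for a 30-voxel target and a large comparison region are also assumptions.

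Most of this stands, and it rules out three stronger readings that a reader might infer:

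- *That any brain-wide drop would be reported as control.* Drops shared by the arms or present equally at rest cancel, and pulse and respiration correction removes part of the rest.
- *That the purpose cannot be met.* Item 1 offers the approach as a tool for probing neurobiology, and the symptom correlation and the resting connectivity analysis in 13.C.iii also bear on it.
- *That the information is thrown away.* Item 13.A.iv masks the maps to compute an average. It does not say that the whole-brain maps are discarded.

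The reply does not close the gap in the fourth row of Step 1. Physiologic noise correction does not remove a learned change in neural state. The connectivity analysis uses resting data, so it cannot show whether the drop in the down-regulate block was regional.

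**Conclusion.** The point holds in a limited form. As planned, a positive control-task result supports an NF-versus-sham difference in target signal. Attributing it specifically to the amygdala, or reading the NF-only correlation as an amygdala mechanism, needs a comparison that the plan does not contain. The gap lies in 13.A.iv, 13.B.i, 13.C.i and 13.C.ii; item 1 only states the purpose they serve.

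The 21%, 48% and 86% show how readily the target test would pass a wholly non-specific NF-only shift of 0.3, 0.5 or 0.8 SD with 30 per arm. They are conditional on that shift and do not estimate how often it would occur. The test of symptoms against sham is unaffected. The change is worth making because it is cheap and because choosing a comparison region after seeing the data would be much less convincing.

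**What to change.** 1. **13.C.i:** keep the target test as the main analysis.
2. **13.A.iv:** from the same down-regulate beta maps, also compute the mean over a prespecified comparison region, for example grey matter outside the amygdala.
3. **13.C.i, secondary:** report the group-by-time estimate and confidence interval for the target, the comparison region, and target minus comparison, side by side.
4. **13.C.ii, secondary:** also correlate symptom change with change in the comparison region.
5. **Interpretation:** attribute the effect specifically to the amygdala only where the target-minus-comparison estimate supports it. Otherwise state that specificity was not established. Do not declare the change non-specific; Step 4 shows how often that would be wrong.

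The cost is plan wording and one extra average from maps already produced, with no new scans. There are two limits to state in the plan. If coupled regions also fall with successful regulation, the difference understates the amygdala effect, which is why the target test stays primary. A whole grey-matter mean would also not detect a change confined to a few limbic regions, so support on the difference would not by itself prove that the effect is confined to the amygdala.

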 Arch Gen Psychiatry **44**(11): 970-975, 1987

4. **Research Plan:** Summarize the study design and research procedures using non-technical language that can be readily understood by someone outside the discipline. **Be sure to distinguish between standard of care vs. research procedures when applicable, and include any flowcharts of visits specifying their individual times and lengths.** Describe the setting in which the research will take place.

A. Screening and Initial Clinical Assessment:

Prior to participation, subjects will be screened both over the phone and in-person at the West Haven campus of the VA Connecticut Health Care System to determine eligibility and to collect demographic and personal history data relevant to the study. If deemed eligible and willing to participate, subjects will attend an initial clinical assessment (see Figure 1 for flowchart of all patient visits). During this assessment, a clinical psychologist with experience with PTSD will evaluate the severity of the subject's symptoms of PTSD and other disorders via a structured clinical interview. If it would represent a significant burden to the participant to attend an initial in-person screening session due to distance or risk of infection by COVID19, a virtual screening will be offered. Assessments that may be collected remotely include the neurological and psychiatric evaluation interview, assessment of treatment history, and, for eligible subjects only, the scripting of life events and the strategy session. If subjects remain eligible after the initial session, they will be invited to continue in the study. Using virtual screening sessions will help to reduce burden on potential participants and staff, and limit in-person visits to only those subjects already determined to meet the psychiatric eligibility criteria.

In the Initial Clinical Assessment, if the subject meets clinical inclusion criteria for PTSD, the clinician will then collect information about the subject's traumas and stressful life events. The collection of life events will occur at the West Haven VA or virtually. At this visit, participants who appear in person will be asked to wear a portable physiotracking watch to record their GSR and Heart rate during memory recall (E4 Wristband, Empatica Inc.) The information about events will later be used to create two types of provocative auditory stimuli: auditory trauma narratives (scripts) and clips of trauma-related noises. Briefly, and in collaboration with the subject, narratives of the subject's six most traumatic and stressful life events will be created and ranked from most to least traumatic. Then, two different scripts will be written for each trauma memory (i.e., different wordings, descriptions). These scripts will be rich in imagery, combining the subject's narrative accounts with descriptions of their emotional and physiological state at the time of the trauma (e.g., sweaty hands, tense muscles, etc.). Once written, scripts will be recorded by different voices and edited so that each

[figure not shown]

Figure 5: Flowchart of study design. All patients are debriefed and unblinded after the final Full Clinical Assessment. Those who had the sham intervention will be offered the option of also participating in NF, but data obtained from unblinded crossover patients will not be used for any of our primary analyses.

lasts exactly 60 seconds. In addition, for each trauma memory described by the subject, recordings of relevant sounds will be collected and combined into 60 second audio clips of trauma-related noises. For example, for a veteran whose trauma involves a jeep under fire, we will concatenate jeep sounds, gun shots, heavy breathing, skidding sounds, moaning, etc. to create a 60s trauma-related sound clip. Both types of minute-long provocative sound files will be played during the scanning runs to provoke trauma recall and anxiety. The two different types of provocative sound clips ensure that we have many different stimuli so we don't need to repeat stimuli too many times (which could induce habituation or "tuning out" to that particular sound clip). Information regarding how these auditory clips are used during scans is outlined in more detail in the following paragraphs.

B. Strategy Development Session:

After the Initial Clinical Assessment, participants will meet in person or virtually with a clinician to take part in a strategy development session, the goal of which is to develop an individualized cognitive strategy for the subject that may provide them with some initial control over their amygdala activity. While strategies discussed during this session are intended to assist individuals in raising/lowering amygdala activity after trauma recall, they are meant only to engender an initial, limited ability to control the amygdala – a starting point for the feedback sessions. During the feedback sessions, subjects will have the chance to experiment with their cognitive strategies and receive direct feedback regarding what is more effective, thereby allowing subjects to develop increasing control over the amygdala in the way that best fits her/his individual style of coping. It is important to note that because this stage occurs before randomization, *all* subjects (NF and sham) participate in this session. Therefore, learning effects specific to the session are controlled for by group comparisons.

C. MR Imaging:

At this point, subjects are ready to begin the MRI portion of the study, which consists of two in-magnet assessments and three neurofeedback or sham sessions, all taking place at the Magnetic Resonance Research Center in the Anlyan Center in New Haven, CT. The specific in-magnet procedures are described in more detail in the following sections *i.* – *iv.*

All subjects who take part in MR imaging are screened at each visit, using screening conventions that are standard for magnetic resonance studies, to ensure they do not have any metallic implants, shrapnel, pacemakers, etc. Subject will be screened to make sure they are not under the influence of illicit substances using urine analysis and a breathalyzer. Based on the results of the urine test and breathalyzer, the researchers will determine whether to run the participant through the study protocol that day or to postpone participation to a later date as to avoid a potential dampening of study effectiveness due to intoxication. Women of child-bearing age will only be included if they assure us they are not pregnant. A free urine pregnancy test will be offered to them to use privately if they wish.

Before each in-magnet assessment, subjects also undergo brief clinical assessments at the Yale Magnetic Resonance Research Center (MRRC). During these sessions, symptoms of PTSD and depression will be collecting using brief self-report checklists. Information regarding any adverse event will also be solicited and recorded.

Subjects will be escorted to and from the scanner by research personnel who will remain present throughout the entire assessment. Before each in-magnet assessment, participants will be required to fill out an MR Safety Questionnaire, endorsing no rule-outs for MR imaging, and walk through a metal detector to ensure they have no ferromagnetic metals on or in their person. The United States Food and Drug Administration (FDA) guidelines for magnet strength and exposure to radio waves will be carefully observed during all scanning sessions. During in-magnet assessments, MR imaging of the brain will record the three dimensional anatomy of the brain, using conventional 3D gradient echo sequence to obtain high-resolution slices of the brain. Images of the subject's brain will also be taken while subjects engage in a specific task (described in more detail in Section III.B.). Thousands of images will be obtained on each subject for each scanning session. This will provide enough information to calculate which regions alter their MRI signal during the activation, or to examine which regions vary in signal level in a correlated manner. We may also collect diffusion tensor imaging (DTI) data which is most commonly used to examine the integrity of white matter tracts. The total imaging time in a single scanning session will not exceed 90 minutes for any subject. During MR scans, components of the Siemens Physiologic Monitoring Unit will be used to take recordings of the subject's pulse (via a pulse-oximeter placed on their finger), respiration (via a pneumatic belt), and galvanic skin response (via sensors on the fingers). This equipment is designed to be completely MR compatible. The records of pulse and respiration will be used during data processing to remove physiologic noise from the images. In order to minimize subject head motion during the MR scans, we may place tape across the subject's forehead or chin. This provides tactile feedback about head motion.

Over the course of this procedure, subjects will be asked to report various aspects of their experience – this will include responding to questions regarding their perceived control over their brain activity.

- i. In-Magnet Assessment 1: MPRAGE, Resting State, Initial Control Runs, and Localizer. If time allows, DTI data will also be collected.

During the first in-magnet assessment, a high resolution structural image will be collected using an MPRAGE sequence. Functional resting state data will be collected, as well as four control runs. During the resting state sessions spontaneous pupil dilation will be measured using a Eyelink 1000 system. As seen in Figure 2, control runs involve a resting period, exposure to a provocative audio clip, a period of down-regulation where participants try to bring down their amygdala activity, and a final resting period. In order to minimize anticipation and rumination regarding the upcoming or preceding stressor, resting periods are separated from the provocative audio clip and subsequent period of down-regulation by a 1-back memory task (seen in Figure 2 as “1-bk”). These memory tasks provide a cognitively-engaging distraction for the subject, preventing anticipatory and spill-over amygdala activity during resting periods and allowing for a more valid baseline to be established.

Rest	1-bk	Prov audio clip	Down-regulate	1-bk	Rest
60s	30s	60s	60s	30s	60s

Figure 2: Schematic illustration of a control task run. Control assessed based on activity in the target region of the amygdala in the down-regulate blocks (relative to rest)

Three localizer runs will also be performed during this session. As seen in Figure 3, the localizer runs will involve a resting period, exposure to a provocative audio clip, and a final resting period. As in the control run, to ensure that resting periods are not affected by the symptom provocation, subjects will perform a 1-back working memory task between the rest periods and the provocative audio clips. In order to identify the part of the amygdala involved in trauma-related anxiety, activation during the trauma exposure will be compared to activity during the resting periods. The area of the amygdala located during this session will be used as the target for the brain activity that will be shown to subjects in future NF runs. As such, we must be able to identify adequate activation in the amygdala for NF to be possible – if no such activation can be identified, the subject will no longer be eligible for continuation of the study.

Rest	1-bk	Prov audio clip	1-bk	Rest
80s	40s	60s	40s	80s

Figure 3: Illustration of a localizer run. Activity will be contrasted between provocation and rest blocks to identify region of peak amygdala activity.

- ii. Randomization

All subjects who remain eligible following the localizer will be randomized to receive either NF or sham feedback, subject to the restriction that there must always be at least as many subjects in the NF group as in the sham group. We will not explicitly describe the sham feedback procedure to subjects – rather, all subjects will be told that they will be randomly assigned to receive either an experimental intervention (that we hope will help symptoms, but that has not yet been demonstrated to be effective) or a control intervention (that we do not believe can help symptoms). Subject will be blind to their condition until study completion, at which point we will tell them which intervention they received. At that point, those who received the control intervention (sham) will be given the option of trying the experimental intervention (NF).

It is important to note that all clinical assessments performed after randomization are carried out by a clinical psychologist who is blind to subject assignment.

iii. Neurofeedback and Sham Feedback

After randomization, subjects will undergo a total of 18 NF or sham feedback runs, carried out over three separate sessions one half of a week apart from one another. Each session tends to be composed of 6 NF or sham runs. However, extenuating circumstances (e.g., technical errors, subjects' schedules) may necessitate the 18 NF or sham runs to be spread out over more than three sessions.

In NF runs, an arrow at the top of the screen indicates the subject's current goal. A red arrow pointing upward prompts the subject to listen to the provocative auditory clip and *not* try to control their brain activity pattern. A blue arrow pointing downward prompts the subject to try to decrease activity in the target area. A white arrow pointing to the right indicates a rest period. In all blocks, a color-coded feedback line is presented below the arrow. The line is updated every 2 seconds throughout the scan to indicate activity in their target area. During the red block, a provocative audio clip is playing. Subjects are instructed not to try to control their activity during this period. The provocative auditory stimulus ends when the blue block begins, but subjects often have high activity in this period due to rumination. Their goal is to decrease this activity during the blue period. Before engaging in this task, subjects are given instructions about what to do during each block, and are informed that there is a 6-8 second delay between changes in activity in their target brain area and changes in the line graph due to the slow blood flow response and processing delays.

